### **5.2 Secondary & Exploratory Efficacy Analyses**

The secondary analyses will be conducted using MMRM method for continuous response variables and ANCOVA with robust regression for complete cases for the PP population and may also be conducted for the ITT population.

As a secondary analysis, the following covariates will be added to the primary endpoint model with baseline score and analyzed the same way: treatment, age, gender, site type, and race included in the model. If covariates are not statistically significant, they may be dropped from the final model.

The secondary and exploratory measures of efficacy including percentage change from baseline in HAM-D6, QIDS-SR16, PHQ-9, GAD-7, CGI-S, change in EuroQol (EQ-5D-5L), and change in SF-36 will be analyzed the same way as for the primary efficacy variable above with baseline score included in the model. The secondary measures of efficacy will also be analyzed with baseline score, treatment, gender, site type, age, and race included in the model. If covariates are not statistically significant, they may be dropped from the final model.

Percentage of responders for HAM-D17, HAM-D6, QIDS-SR16, PHQ-9, GAD-7, CGI-S, CGI-I, CGI-EI, and SF-36, and remitters for HAM-D17, HAM-D6, QIDS-SR16, PHQ-9, GAD-7, and CGI-S will be analyzed by visit, separately, using a Generalized Linear Mixed model. Pre-specified covariates may be added.

Percentage of patients on congruent and incongruent medications will be compared between GEN and TAU using Chi-square tests at each time point.

Medication compliance using BARS and prescription filling data will be summarized and compared between treatment groups (see 7.6 for description).

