### **3.3 Covariates**

Baseline HAM-D17 score is a covariate for the primary analysis. For secondary and exploratory analyses, the following covariates may be added to the model with baseline score: Age, Gender, Treatment, and Site Type (PCP/Psych).

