## **5 EFFICACY ANALYSIS**

### **5.1 Primary Efficacy Analysis**

The primary measure of efficacy is the percentage change from baseline to week 8 in HAM-D17. The percentage change from baseline in HAM-D17 will be analyzed using a Mixed Model for Repeated Measures (MMRM). The model will include treatment, week (4 & 8), treatment-by-week interaction, baseline HAM-D17 score, baseline HAM-D17-by-week interaction as fixed effects. Unstructured covariance between measurements at weeks four and eight, from the same patient, will be incorporated into the model. If there is a convergence issue, Toeplitz covariance will be used. The MMRM method employed here is known as Maximum Likelihood (ML) to effectively handle the missing values as discussed in Section 3.4. The p-value will be derived from the T-test for comparing two treatment arms at week 8 (treatment by week interaction term). If overwhelming evidence suggests that the normality assumption is not satisfied, complete case analyses (CCA) of the primary efficacy endpoint will be conducted for the PP population for the completers of week eight. The primary endpoint will be analyzed by fitting an analysis of covariance (ANCOVA) model which includes baseline HAMD-17 score. Robust regression method (M Estimation Method by Huber) will be used for CCA to detect potential outliers and appropriately weigh the influence of the outliers should they exist.

As a sensitivity analysis, complete case analyses (CCA) of the primary efficacy endpoint will be conducted for the PP population for the completers of Week 8. The primary endpoint will be analyzed by fitting an analysis of covariance (ANCOVA) model which includes treatment, baseline HAMD-17 score, age, and gender. If age and gender are not statistically significant, they may be dropped from the final model. Robust regression method (M Estimation Method by Huber) will be used for CCA to detect potential outliers and appropriately weigh the influence of the outliers should they exist.

The above MMRM and CCA analyses will also be conducted for the ITT population.

The primary methods for checking the normality assumption will be through graphical assessment using a Q-Q plot and histogram of the residuals. If the points for the Q-Q plot are approximately linear and if the histogram is approximately bell-shaped, the residuals will be considered normally distributed.

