## **6 SIGNIFICANCE LEVEL**

A significance level of 0.05 (2-sided) will be used. All analyses will be performed using IBM SPSS Statistics 25 and/or SAS 9.4 and/or JMP 14.

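### Non-significant covariates may be dropped at the analyst's discretion in the sensitivity ANCOVA and the adjusted supplementary models; the effect is small and the fix is free

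*SAP*

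**What the plan says.** **Primary model (SAP 5.1).** The terms are fixed: "The model will include treatment, week (4 & 8), treatment-by-week interaction, baseline HAM-D17 score, baseline HAM-D17-by-week interaction as fixed effects". No dropping rule is attached.

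**Complete-case sensitivity ANCOVA (SAP 5.1).** This starts with treatment, baseline HAM-D17, age and gender. Then: "If age and gender are not statistically significant, they may be dropped from the final model".

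**Adjusted models (SAP 5.2).** The primary endpoint is to be re-analysed with further covariates: "analyzed the same way: treatment, age, gender, site type, and race included in the model". For the other measures: "The secondary measures of efficacy will also be analyzed with baseline score, treatment, gender, site type, age, and race included in the model". Each of these statements is followed by the same permission: "If covariates are not statistically significant, they may be dropped from the final model".

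**Covariates section (SAP 3.3).** For secondary and exploratory analyses, "the following covariates may be added to the model with baseline score: Age, Gender, Treatment, and Site Type (PCP/Psych". Race is absent, and adding the covariates is optional.

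**Significance level (SAP 6).** "A significance level of 0.05 (2-sided) will be used".

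**The concern.** A covariate-adjusted analysis is most useful when its terms are fixed before the outcomes are seen. Here a covariate stays or goes according to its p-value in the same data that estimate the treatment effect. The rule is also permissive: two analysts following the SAP could report different final models, and both would comply. That weakens analyses whose purpose is to show that the primary result does not depend on modelling choices.

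The covariate list is itself unsettled. SAP 3.3 makes the covariates optional and omits race, whereas 5.2 says they will be added and includes race. A programmer cannot derive a single adjusted model from the two sections. SAP 1.2 states that the SAP supersedes the protocol's analysis plan, so the protocol cannot settle the matter.

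**Working it through.** The plan states no figure on this point. The check therefore has two parts: which models the rule reaches, and how much it could matter.

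**1. Reach of the rule**

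| Model | Where | Dropping permitted? |
|---|---|---|
| Primary MMRM | 5.1 | No, terms fixed |
| Complete-case sensitivity ANCOVA | 5.1 | Yes, age and gender only |
| Baseline-only models of continuous secondary and exploratory measures | 5.2 | No, analysed as the primary |
| Adjusted model of the primary endpoint | 5.2 | Yes, no term protected |
| Adjusted models of the other continuous measures | 5.2 | Yes, no term protected |
| Responder and remitter models | 5.2 | No (covariates may be added) |
| Adverse-event model | 5.3 | No, terms listed |

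The permission thus appears in three sentences: one in 5.1 and two in 5.2.

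**2. Size of the effect**

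Inputs from the documents:
- 190 per arm and 16.7% discontinuation by Week 8 (protocol section 10.0), so 190 × (1 − 0.167) = 158 per arm.
- Two-sided alpha of 0.05 (SAP 6).
- Two droppable covariates in the 5.1 ANCOVA (age, gender), and four in the 5.2 models once treatment and baseline are kept (age, gender, site type, race).

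Assumptions not in the documents: covariate effects between 0 and 0.20 SD, and ordinary least-squares ANCOVA standing in for the MMRM.

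Null trials with two arms of 158 were simulated, and the treatment test was taken at 0.05 under three rules:
- *Fixed*: keep every covariate.
- *Automatic*: drop every covariate with p ≥ 0.05, with no choice.
- *Discretionary*: drop any selection of the non-significant covariates, choosing the one that most favours significance. This is the worst case that the text permits.

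| Droppable covariates | Assumed effects | Fixed | Automatic | Discretionary | Discretionary − fixed |
|---|---|---|---|---|---|
| Two | non-zero | 4.8% | not run | 5.2% | 0.4 |
| Two | none | 5.0% | not run | 5.4% | 0.4 |
| Four | non-zero | 4.5% | not run | 5.0% | 0.5 |
| Four | none | 4.7% | not run | 5.5% | 0.8 |
| Four | 0.10 to 0.20 SD | 5.0% | 5.0% | 5.8% | 0.8 |
| Four | none | 5.2% | 5.1% | not run | – |
| Four | 0.10 to 0.15 SD | 5.3% | 5.5% | not run | – |
| Four, several settings | 0 to 0.20 SD | 4.9–5.1% | 5.0–5.3% | 5.2–5.9% | about 0.3 to 0.8 |

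In the last row the difference comes from the ends of the ranges: 5.2 − 4.9 = 0.3 and 5.9 − 5.1 = 0.8. With 10,000 trials the Monte Carlo standard error is √(0.05 × 0.95 / 10,000) = 0.2 points, so the change between rules matters more than the level in any one cell.

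Automatic dropping moves the error rate by no more than simulation noise. The increase comes from the freedom to choose.

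**3. What dropping gains**

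With 316 participants, a model with intercept, treatment and baseline leaves 313 residual degrees of freedom. Four more single-degree covariates leave 309, a loss of 4/313 = 1.3%. Race with more than two categories would use slightly more. Keeping the covariates costs almost no precision, so the option to drop them buys nothing.

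**The case against.** The strongest reply is that nothing confirmatory is touched. The primary MMRM is fixed, and each continuous secondary measure has a fixed baseline-only analysis beside the adjusted one. The complete-case ANCOVA mainly probes missing-data handling (SAP 3.4 compares it with the likelihood results) and outliers (5.1 uses Huber M-estimation). Leaving out two non-significant covariates hardly harms either purpose. All of this stands and limits the point to supplementary models.

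Four stronger readings are tempting, and the documents do not support them:

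- *Treatment itself may be dropped.* Both 3.3 and 5.2 list it among the covariates, and 5.2 exempts nothing. But treatment is already a term of the primary model that 5.2 extends, and the 5.1 rule names only age and gender. Applied literally, the rule could remove the estimate in 95% of null trials (1 − 0.05) and leave no comparison to report. It reads as a drafting slip.
- *The plan's 5% error rate is lost.* The primary test has no dropping rule, and automatic dropping does not raise the error rate materially elsewhere.
- *Inflation reaches 6.0% to 8.5%.* Such figures arise when any covariate subset may be chosen, including one that omits significant covariates. The text allows only non-significant ones to go.
- *The analyst will choose with the treatment p-value in view.* The word *may* leaves this open, but no section describes the order in which results are inspected.

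**Conclusion.** The point holds for the 5.1 sensitivity ANCOVA and the 5.2 adjusted models of continuous outcomes. Their final form is left to discretion exercised on the outcome data, where a fixed covariate set would do the job at no cost. The worst case within the text is an increase of roughly 0.3 to 0.8 percentage points over a 5% type I error. That rests on 158 per arm, assumed covariate effects of 0 to 0.20 SD, and least squares in place of the MMRM. Stronger covariates would more often stay significant and leave less to drop. The mismatch between 3.3 and 5.2 is a plain inconsistency that needs no calculation. This is a free improvement and does not threaten the primary conclusion.

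**What to change.** Amend the SAP as follows:

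1. Delete all three sentences that permit dropping: one in 5.1, two in 5.2.
2. In the 5.1 sensitivity ANCOVA, keep treatment, baseline HAM-D17, age and gender whatever their p-values.
3. In every adjusted model under 5.2, keep baseline score, age, gender, site type and race whatever their p-values.
4. In 3.3 and 5.2, name treatment as the tested effect and take it out of the covariate lists.
5. In 3.3, add race and state that the listed covariates *will be included* in the adjusted models. Bring the optional wording for the responder and remitter models in 5.2 into line in the same edit.

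The cost is SAP wording only. No data collection, sample size or primary analysis changes, and the loss of precision is about 1%.

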##### **2.1.2.1 Evaluate the following for GEN vs TAU:**

- Percentage of responders in HAM-D17 at Week 8 in each treatment group (see definition in 7.1)
- Percentage of remitters in HAM-D17 at Week 8 in each treatment group (see definition in 7.2)

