##### **2.1.2.2 Evaluate the following for GEN vs E-GEN:**

- Mean percentage change from baseline in HAM-D17 at Week 8
- Percentage of responders in HAM-D17 at Week 8
- Percentage of remitters in HAM-D17 at Week 8

**The treatment groups used for all subsequent analyses (all scales at each time point) will depend on the results in 2.1.2.2**

- If GEN is not statistically different than E-GEN at any endpoint, GEN and E-GEN treatment arms will be combined and compared to TAU
- If E-GEN is statistically superior to GEN at any endpoint, E-GEN will be compared to TAU
- If GEN is statistically superior to E-GEN at any endpoint, GEN will be compared to TAU

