### **3.4 Missing Data**

Missing observations of response variables will be checked and missing patterns by treatment and overall will be described including a CONSORT trial flow diagram. Missing values will be handled by using maximum likelihood method (ML). Complete cases analyses will be conducted and results will be compared to those obtained from ML. The main analysis conclusion at Week 8 will be drawn using ML method for the PP population (see Section 5.1).

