## **7 APPENDIX**

### **7.1 Definition of Responders**

For HAM-D17, HAM-D6, QIDS-SR6, HAMD-6, PHQ-9, GAD-7, SF-36, a responder is defined as a participant with 50% decrease from baseline in total scale score.

For Clinical Global Impression: Severity of Illness CGI-S: a responder is defined as a decrease in category of severity of at least 1 point, for Clinical Global Impression: Global Improvement CGI-I: it's defined as a score from 1 to 3, and for Clinical Global Impression: Efficacy Index CGI-EI: it's defined as scores of 01, 02, 05, or 06.

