### **7.2 Definition of Remitters**

A remitter is defined as a participant at a post-treatment visit with HAM-D17  $\leq 7$ , HAM-D6  $< 5^2$ , QIDS-SR6  $\leq 5$ , PHQ-9  $< 5$ , GAD-7  $< 5$ , or CGI-S  $\leq 1$ .

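### Week 8 response and remission are modelled one visit at a time, so patients without a Week 8 score drop out of these analyses and their Week 4 score goes unused

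*SAP*

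**What the plan says.** SAP 3.4 makes a general commitment: "Missing values will be handled by using maximum likelihood method (ML". It adds that complete-case results will be compared with it, and it ties the main Week 8 conclusion to the primary analysis. SAP 5.1 puts the commitment into practice: "The MMRM method employed here is known as Maximum Likelihood (ML) to effectively handle the missing values". That model takes Weeks 4 and 8 jointly.

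SAP 5.2 then divides the endpoints by type. For continuous outcomes, "The secondary analyses will be conducted using MMRM method for continuous response variables". Responders and remitters instead "will be analyzed by visit, separately, using a Generalized Linear Mixed model", and covariates are optional.

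The definitions do not address a missing score. In SAP 7.1, "a responder is defined as a participant with 50% decrease from baseline in total scale score"; in SAP 7.2, "A remitter is defined as a participant at a post-treatment visit with HAM-D17" at or below 7. Neither says how to classify a patient who was not assessed. The protocol's section 16.1 had imputation, but SAP 1.2 states that the SAP replaces the protocol's analysis plan.

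The first item in the ordered secondary list (SAP 2.1.2.1, GEN against TAU) is "Percentage of responders in HAM-D17 at Week 8 in each treatment group", followed by remission. The same two endpoints are two of the three in the GEN against E-GEN step, of which SAP 2.1.2.2 says: "The treatment groups used for all subsequent analyses (all scales at each time point) will depend on the results in 2.1.2.2".

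**The concern.** A model fitted to one visit sees only patients observed at that visit. A patient who leaves after Week 4 informs the Week 8 percentage change through the MMRM but not Week 8 response or remission. Two analyses of one scale, at one time point, therefore rest on different missing-data assumptions. The binary model is valid if missingness depends only on covariates it contains. The Week 4 outcome is not among the covariates listed in SAP 3.3.

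If leaving depends on early improvement, and does so differently by arm, the response difference is distorted. These endpoints come first among the secondary tests. They also help decide whether GEN and E-GEN are pooled, so an error here would carry into every later comparison.

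**Working it through.** The plan gives no figure of its own on this point. The check needs only the planned arm size and discontinuation rate (Protocol 10.0), not the derivation of the total.

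**Patients affected.** 190 × 0.167 = 31.7 per arm, leaving 190 × 0.833 = 158.3. In total 570 × 0.833 = 474.8, so about 95 of 570 are absent. This takes every discontinuer by Week 8 as lacking a Week 8 score.

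**False difference when there is no true effect.** Assumed, not from the documents: true Week 8 response 26.5% in both arms; standardised Week 4 and Week 8 improvement bivariate normal with correlation ρ of 0.5 or 0.65; logit of dropout linear in Week 4 improvement x with slope 0.35 or 0.7 per SD, and intercept set to give 16.7%. With π(x) the dropout probability, φ and Φ the standard normal density and distribution function, and t the response threshold, the rate among those observed is

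p_obs = ∫φ(x)[1 − π(x)]Φ((ρx − t)/√(1 − ρ²))dx ÷ ∫φ(x)[1 − π(x)]dx.

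Type I error is Φ(d/SE − 1.96) + Φ(−d/SE − 1.96), where d is the difference in p_obs and SE² = Σ p_obs(1 − p_obs)/158.3. The table gives d in percentage points and the type I error.

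| ρ | slope | non-improvers leave one arm; dropout random in the other | opposite mechanisms in the two arms |
|---|---|---|---|
| 0.50 | 0.35 | 0.91; 5.4% | 1.88; 6.7% |
| 0.65 | 0.35 | 1.17; 5.6% | 2.45; 7.8% |
| 0.50 | 0.70 | 1.67; 6.3% | 3.58; 11.2% |
| 0.65 | 0.70 | 2.12; 7.1% | 4.65; 15.6% |

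Worked line (0.65, 0.70, one arm): p_obs is 28.62% against 26.50%, so d = 2.12 points. SE = √(0.2862 × 0.7138/158.3 + 0.265 × 0.735/158.3) = 0.0502 and d/SE = 0.42. The error is Φ(−1.54) + Φ(−2.38) = 0.062 + 0.009 = 0.071.

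With the same mechanism in both arms d is zero, but at this setting each rate is overstated by about 2 points.

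**When there is a true effect.** A simulation of 4,000 trials assumed 190 per arm, SD 35 for percentage change, correlation 0.6, dropout slope 1 per SD and about 16.5% dropout. True response was 33.9% against 23.7%, a difference of 10.2 points.

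| dropout | by-visit difference | joint model on binary Week 4 and 8 response |
|---|---|---|
| completely at random | 10.1 | 10.1 |
| non-improvers leave both arms | 10.7 | 10.5 |
| non-improvers leave TAU only | 7.8 | 8.8 |
| non-improvers leave GEN only | 13.1 | 11.8 |

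In every row, maximum likelihood on the continuous score recovered the true mean difference (10.4 to 10.5).

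**Which remedy works.** In the last two rows the joint binary model takes the bias from −2.4 to −1.4 and from 2.9 to 1.6, removing 1.0/2.4 = 42% and 1.3/2.9 = 45%. In the no-effect case at ρ = 0.65 and slope 0.7, with Week 4 response assumed to be 18%, it takes 2.12 to 1.07 (50% removed) and 4.65 to 1.99 (57%). Dichotomising Week 4 discards information that predicts dropout. Imputing from the continuous Week 4 score brought the no-effect differences to within 0.03 points of zero.

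**The case against.** - **The SAP contradicts itself.** A reader might infer this from SAP 3.4 and 5.2. The text does not go that far: SAP 3.4 points to SAP 5.1, SAP 5.1 equates maximum likelihood with the MMRM, and SAP 5.2 keeps the MMRM for continuous variables. A single-visit model is also a likelihood fit, though to observed cases only. What stands is that a general commitment is not carried through to the binary endpoints.
- **One longitudinal model reported by visit may be intended.** The wording about separate visits argues against it. The random effect is not named, and a patient effect cannot be identified from one binary record each. If a joint model is meant, the SAP must say so.
- **The per-protocol set may already exclude these patients.** SAP 3.2.1 requires the Week 8 visit to fall within 48 to 64 days of baseline. Read literally, patients without that visit are out, and the contrast with the MMRM largely disappears in that set. SAP 5.1, however, treats Week 8 completers as a subset of the per-protocol population. The ambiguity is real, and it does not affect the ITT set.
- **Arm-specific dropout is speculative.** Participants and the central HAM-D17 raters are blinded (Protocol 5.0 and 13.0). The treating clinician is not, and Protocol 14.1.2 lets the investigator withdraw patients. Differential dropout is therefore possible, but nothing in the documents makes it expected or supports opposite mechanisms.
- **The MMRM is not immune.** It is unbiased only under missing at random and a correct model. Patients lost before Week 4 have no Week 4 score for any method to use.

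**Conclusion.** The point stands as a weakness in a stated method, and it should be corrected. As written, Week 8 response and remission are in effect complete-case analyses that set aside a collected and relevant Week 4 score, for about 32 of 190 patients per arm at the protocol's own rate.

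The documents do not show that the response comparison will be biased, though a reader might infer it. With no true effect there is no bias in the difference when dropout is completely at random or follows the same mechanism in both arms; with a true difference of 10.2 points, a common mechanism moved it by only 0.5. Under one-arm dependence on Week 4 score, the false difference is about 1 to 2 points with type I error 5.4% to 7.1%. Opposite mechanisms give 3.6 to 4.7 points (11% to 16%) at the steeper slope and 1.9 to 2.45 points (7% to 8%) at the shallower one; this is an extreme case. The correlation, slope and response rate behind these sizes are assumptions; only the arm size and the 16.7% come from the trial.

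**What to change.** 1. In SAP 5.2, make the main Week 8 response and remission analysis one based on multiple imputation of HAM-D17 scores. Use treatment, baseline and Week 4 score so that it matches the MMRM, derive response and remission from each imputed score, and combine the results across imputations.
2. Keep the by-visit observed-case model as a sensitivity analysis.
3. Do not rely on a repeated-measures logistic model of dichotomised Week 4 and Week 8 response as the main remedy, since it removes only about half the bias.
4. State in SAP 3.2.1 that patients with no Week 8 visit remain in the per-protocol set, and apply the same approach to the ITT set.

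The cost is SAP wording and modest extra programming, with no change to visits, data collection or sample size. The analysis will rest on a missing-at-random assumption, as the MMRM already does.
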